## 4 STUDY DESIGN

### 4.1 Study Description

This study is a randomized immunogenicity study in an enrolled cohort with active surveillance for acute respiratory illness (ARI). During this study, participants will be randomly assigned to receive an approved quadrivalent influenza vaccine (Flucelvax [cclIV4]) and mRNA COVID-19 vaccine (Moderna) either concomitantly (given in contralateral arms) or sequentially (28 days apart).

Blood samples from participants will be collected for measurement of biomarkers of immune response at baseline (visit 1; day 0), post-vaccination 1 (visit 2; day 28), post-vaccination 2 (visit 3; day 56), and post-season (visit 4; day 180). Serum and peripheral blood mononuclear cells (PBMC) and plasma (target to collect PBMC and plasma samples at every visit from a subset of approximately 250 participants; 200 adults and 50 children) samples will be isolated from whole blood and tested for biomarkers of vaccine immunogenicity, and duration of antibody responses.

Participants will receive electronic surveys via email or text message three days after each vaccination asking about vaccine reactogenicity and weekly asking about change in health status and new ARI symptoms; those reporting illness may be asked to provide a respiratory swab for laboratory testing for influenza and SARS-CoV-2 and up to 2 additional blood draws (acute [< 10 days after symptom onset] and convalescent [28 days after acute visit if lab-confirmed positive for influenza or SARS-CoV-2]).

## 4.2 Laboratory

Blood samples from participants will be collected for measurement of biomarkers of immune response at Visit 1 (day 0; baseline), Visit 2 (day 28; post-vaccination 1), Visit 3 (day 56; post-vaccination 2), and Visit 4 (day 180; post-season). Sera, PBMC, and plasma samples will be tested for biomarkers of vaccine immunogenicity, duration of antibody responses, and immune response to circulating SARS-CoV-2 variants and influenza virus strains.

## 4.3 Randomization

Permuted block randomization stratified by age group (children aged 6-11 years and adults aged 18-64 years) and site will be used at each site to ensure even allocation to each study arm. At each site, participants will be randomized 2:1:1 to receive: (i) concomitant administration of a mRNA COVID-19 vaccine and a quadrivalent influenza vaccine (cclIV4), (ii) sequential administration of a quadrivalent influenza vaccine (cclIV4) at Visit 1 (day 0) and a mRNA COVID-19 vaccine at Visit 2 (day 28), and (iii) sequential administration of a mRNA COVID-19 vaccine at Visit 1 (day 0) and a quadrivalent influenza vaccine (cclIV4) at Visit 2 (day 28).

The project statistician will generate the randomization schemes which will be uploaded to REDCap. The randomization schedule will not be available to the study staff, so the next randomization allocation will not be known before randomization occurs. Following confirmation of study eligibility criteria during Visit 1, participant randomization will be through REDCap with treatment allocation recorded on the case report form (CRF).

In the event that REDCap is unavailable, participants will be manually randomized through the use of sealed envelopes with randomization allocations enclosed. The project statistician will prepare envelopes that will use the same randomization strategy as the primary scheme embedded in REDCap. When an unblinded team member is informed of the age group, they will pull the next envelope in order. To capture the allocation per subject, a separate form in REDCap will be used by the unblinded study personnel to add the assignment. Sites will need to keep a log capturing these instances. The next available sequential study-number will be assigned to each enrolled participant upon study-entry.

## 4.4 Blinding

Participants will not be blinded to vaccine group and will receive two vaccines in separate limbs (for the concomitant vaccination [group i]) or one vaccine at Visit 1 (day 0) and a second vaccine at Visit 2 (day 28) (for sequential vaccination [groups ii and iii]) in an unblinded manner.

## 4.5 Data Collection and Storage

Data will be handled according to the Duke Vaccine and Trials Unit Standard Operation Procedure (SOP) (DVTU M010). Data will be captured electronically in a REDCap database. The enrollment questionnaire may be administered by research staff or completed online by the participant. Follow-up surveys will be completed online by the participant.

# 6 ANALYSIS POPULATIONS

## 6.1 Intent-to-Treat (ITT)

The ITT population will include any participant who was enrolled and randomized.

## 6.2 Modified Intent-to-Treat (mITT)

The mITT population will include any participant who was enrolled, randomized, and received both vaccines.

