Study Duration:	12 months total Enrollment: Aug — Oct 2023 Vaccination: Aug — Nov 2023 Blood draws: Aug 2023 — May 2024 Active surveillance for illness: Aug 2023 — May 2024 Laboratory testing: Nov 2023 — Jul 2024
Participant Duration and Number of Participants:	
 • Up to 10 months (Aug 2023 — May 2024) • 800 total participants (600 aged 18-64 years, 200 aged 6-11 years) at 4 sites (only two sites will enroll children aged 6-11 years)
Randomization:	Adults aged 18-64 years, 2:1:1 permuted block randomization 
 i. Concomitant cclIV4 + COVID-19 mRNA (day 0) [n = 300] ii. Sequential cclIV4 (day 0), COVID-19 mRNA (day 28) [n = 150] iii. Sequential COVID-19 mRNA (day 0), cclIV4 (day 28) [n = 150]

	
Children aged 6-11 years, 2:1:1 permuted block randomization
 
 i. Concomitant ccIV4 + Moderna COVID-19 mRNA (day 0) [n = 100] ii. Sequential ccIV4 (day 0), Moderna COVID-19 mRNA (day 28) [n = 50] iii. Sequential Moderna COVID-19 mRNA (day 0), ccIV4 (day 28) [n = 50]

Description of Study Procedures:
	
This study is a randomized immunogenicity study in an enrolled cohort with active surveillance for acute respiratory illness (ARI). During this study, participants will be randomly assigned to receive an approved quadrivalent influenza vaccine (Flucelvax [ccIV4]) and mRNA COVID-19 vaccine (Moderna) either concomitantly (given in contralateral arms) or sequentially (28 days apart).
 
Blood samples from participants will be collected for measurement of biomarkers of immune response at baseline (visit 1; day 0), post-vaccination 1 (visit 2; day 28), post-vaccination 2 (visit 3; day 56), and post-season (visit 4; day 180). Serum and peripheral blood mononuclear cells (PBMC) and plasma (target to collect PBMC and plasma samples at every visit from a subset of approximately 250 participants; 200 adults and 50 children) samples will be isolated from whole blood and tested for biomarkers of vaccine immunogenicity, and duration of antibody responses.

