8 STATISTICAL ANALYSIS

8.1 Study Populations

There will be two study populations: the modified Intent-to-Treat (mITT) and Immunogenicity populations. The mITT population will include any participant who was enrolled, randomized, and received at least one vaccine. The Immunogenicity Population is a subset of the mITT Population that includes only subjects who received at least one vaccine, provide visit 1 and visit 2 blood draws available for analysis within the protocol-defined time frame, and with no protocol violations affecting immunogenicity. These protocol violations will be listed in the Statistical Analysis Plan. Statistical analyses of safety outcomes will be performed for the mITT population, and immunogenic outcomes will be analyzed for the Immunogenicity Population.

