### 2.2 Exploratory

EO1: To determine baseline and post-vaccination influenza antibody titers by microneutralization (MN), in a subset of samples, against cclIV4 vaccine antigens following concomitant administration with mRNA vaccine or alone.

EO2: To determine baseline and post-vaccination SARS-CoV-2 antibody binding titers and ACE2 binding inhibition and viral neutralization, on a subset of specimens, against Moderna mRNA COVID-19 vaccine antigens following concomitant administration with cclIV4 or alone.

EO3: To determine duration and rate of waning of influenza HAI and MN antibody titers against cclIV4 vaccine antigens and circulating influenza viruses.

EO4: To determine duration of and rate of waning of SARS-CoV-2 antibody titers and viral neutralization titers, on a subset of samples, against Moderna mRNA COVID-19 vaccine antigens and circulating SARS-CoV-2 variants.

EO5: To determine influenza HAI and MN antibody titers against circulating influenza viruses during baseline and post-vaccination or post-infection.

EO6: To determine SARS-CoV-2 antibody binding titers and viral neutralization titers (in a subset of samples) against circulating SARS-CoV-2 variants during baseline and post-vaccination.

EO7: To compare the frequencies of antigen-specific T and B cells utilizing conventional ELISPOT assays, high-dimensional flow cytometric analysis of innate and adaptive immune cell

phenotype characterization using fluorochrome-conjugated antigen tags, and intracellular cytokine staining to 2023-24 cclIV4 and mRNA COVID-19 vaccines administered either concomitantly or sequentially, 28 days apart.

EO8: To compare transcriptome, B cell receptor (BCR) and T cell receptor (TCR) diversity of antigen-specific cells and assess serological antibody repertoire (clonotypes) using 10X genomics platform, and liquid chromatography/mass spectroscopy in a subset of participants.

EO9: To investigate the waning of antigen-specific B cells and antibody clonotypes in a subset of participants.

EO10: To describe safety of concomitant versus sequential administration of cclIV4 and mRNA COVID-19 vaccination.

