### 8.2 Demographics

Demographic information including age, sex, race, ethnicity, and enrollment site will be presented by treatment group. Summary statistics (e.g., mean, standard deviation, median) will be presented for continuous variables. Categorical variables will be described with frequencies and percentages.

Demographics for the ITT population will be presented.

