### *Safety*

Safety endpoints will be assessed using the mITT population.

Frequency and proportion of participants reporting injection site and/or systemic reactions during the first 3 days following each vaccination visit will be stratified by severity and their impact on health, and reported along with the difference in proportions reporting moderate/severe symptoms between groups and a 95% confidence interval for the difference.

Frequency and proportion of participants reporting a change in health status requiring hospital admission (including a description of the event) during the study period will be reported along with the difference in proportions between groups and a 95% confidence interval for the difference.

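### SAP 6.2 limits the safety population (mITT) to recipients of both vaccines, whereas protocol 8.1 requires at least one; the SAP rule can drop vaccinated participants, most likely from the sequential arms

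*SAP*

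**What the plan says.** Protocol 8.1 defines the set as follows: "The mITT population will include any participant who was enrolled, randomized, and received at least one vaccine". SAP 6.2 defines a set of the same name differently: "The mITT population will include any participant who was enrolled, randomized, and received both vaccines". Neither document explains the change.

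Both documents use the set for safety. Protocol 8.1: "Statistical analyses of safety outcomes will be performed for the mITT population". SAP 9.2, under Safety: "Safety endpoints will be assessed using the mITT population". For reactions, the SAP reports the "difference in proportions reporting moderate/severe symptoms between groups and a 95% confidence interval for the difference", and it treats hospital admissions in a similar way.

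The SAP also defines an ITT population, but the only use it names is in section 8.2: "Demographics for the ITT population will be presented". Safety is one of ten exploratory objectives and is worded descriptively: "EO10: To describe safety of concomitant versus sequential administration of cclIV4 and mRNA COVID-19 vaccination".

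Under protocol 5.1 and Table 1, group i receives both vaccines at Visit 1. Groups ii and iii receive one at Visit 1 and the other at Visit 2, with a window of day 28 to 42. Protocol 5.5.2.1 sends every group a reaction survey 3 days after Visit 1, and protocol 5.5.2.2 asks about hospitalisation weekly until Visit 4.

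**The concern.** Two programmers, one working from the protocol and one from the SAP, would produce safety tables with different denominators under the same label.

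The SAP version also selects on something that happens after exposure. A group ii or iii participant who is vaccinated at Visit 1, reports a reaction or is hospitalised, and never receives the second vaccine is removed together with the event. In group i, removal requires that only one of two injections due at the same visit is given. The selection therefore bears unevenly on the two sides of the comparison.

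The outputs at risk are the reaction tables after Visit 1 and the hospitalisation table. The sequential groups' tables after Visit 2 are barely touched, because anyone given the second vaccine at Visit 2 has already had the first.

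**Working it through.** **1. Does any other text settle the definition?**
- Protocol 8.1 hands to the SAP only the list of violations that affect immunogenicity, not the definition of mITT.
- Protocol 8.2 leaves the description of the exploratory analyses to the SAP, but it does not redefine a population that 8.1 names and assigns to safety.
- Protocol 5.3.6 replaces only participants who withdraw before the first vaccine, so it does not cover loss between the two.
- A second vaccine given early or outside the window (protocol 5.4.3 and 6.3) still counts as both vaccines. A missed window alone therefore removes nobody from mITT.

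The two definitions remain in conflict.

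**2. Planned numbers (Protocol Summary, Randomization).** Splitting 600 adults and 200 children 2:1:1 gives 300/150/150 and 100/50/50, as stated. Concomitant: 300 + 100 = 400. Sequential: 150 + 150 + 50 + 50 = 400. Group ii or group iii alone: 150 + 50 = 200.

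**3. Participants removed.** Let d be the share of sequential participants who miss the second vaccine, and c the share of group i given only one. Both are assumptions. Removed = 400 × d and 400 × c.
- d = 1%: 4 sequential participants. d = 2/5/10%: 8/20/40, leaving 392/380/360 of 400.
- c = 0: all removals are sequential.
- c = 0.5% (2 people): the sequential share is 8/10, 20/22 and 40/42, that is 80/91/95%, for d = 2/5/10%.
- c = d = 1%: 4 against 4, so no imbalance.

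Removals fall mainly on the sequential side whenever d exceeds c.

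**4. Possible shift in the sequential first-dose rate.** Let p be the true moderate/severe reaction rate after the first vaccine, m the overall share missing the second (d above), and RR the relative risk of missing it in reactors. Then:
- share missing among non-reactors: b = m / (p × RR + 1 − p)
- share missing among reactors: a = RR × b
- rate seen under the SAP rule: p × (1 − a) / (1 − m)

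Example with p = 30%, m = 10%, RR = 3: b = 0.10/1.6 = 0.0625, a = 0.1875, rate seen = 0.30 × 0.8125/0.90 = 27.08%, a shift of −2.92 points.

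| m | RR | p = 10% | p = 20% | p = 30% |
|---|---|---|---|---|
| any | 1 | 0 | 0 | 0 |
| 2% | 2 | −0.2 | −0.3 | −0.3 |
| 2% | 3 | −0.3 | −0.5 | −0.5 |
| 5% | 2 | −0.4 | −0.7 | −0.9 |
| 5% | 3 | −0.8 | −1.2 | −1.4 |
| 10% | 2 | −0.9 | −1.5 | −1.8 |
| 10% | 3 | −1.7 | −2.5 | −2.9 |

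Shifts are in percentage points. An RR below 1 reverses the sign. With RR = 0.5, m = 10% and p = 30%: b = 0.10/0.85 = 0.1176, a = 0.0588, rate seen = 0.30 × 0.9412/0.90 = 31.4%, a shift of +1.4.

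**5. Scale.** 95% half-width for a difference = 1.96 × √[p(1 − p)(1/n₁ + 1/n₂)]. At p = 10/20/30%:
- 400 against 400: 4.2/5.5/6.4 points
- 400 against 200: 5.1/6.8/7.8 points

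The largest shift is 2.92/6.35 = 46% of the smaller half-width. SAP 9.2 does not say whether the sequential groups are pooled, so both versions are shown. Groups ii and iii receive different first vaccines, so a pooled first-dose rate is a device for sizing here, not a planned estimate.

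**6. Hospitalisation.** The documents give no rate, so no bias is modelled. One dropped event is 1/400 = 0.25 points of the pooled sequential proportion. Its description would also be missing from the report.

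**The case against.** The strongest reply is that little may turn on this. Safety is exploratory and descriptive, with no safety hypothesis stated. The documents give no missed-vaccine or reaction rate, so both the imbalance and the bias rest on assumptions. The worst case above needs three unfavourable values together and still lies within sampling error. SAP 8.1 will present missed visits and a breakdown of the analysis populations, so the number excluded should be visible. Participants who withdraw may ask for their data to be removed (protocol 5.3.6), so some are lost under either definition. All of this stands and limits the size of the point. It does not reconcile the two definitions, and a count of exclusions does not recover the excluded events.

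Three stronger readings are tempting, and the documents do not support them:
- **The SAP rule makes sequential vaccination look safer.** That requires reactors to be likelier to miss the second vaccine. If they are no likelier, the shift is zero; if they are less likely, it goes the other way.
- **Removals are known to come mostly from the sequential arms.** This is a sound inference from the visit schedule, but no documented rate confirms it.
- **The both-vaccines wording in SAP 6.3 and 6.4 is the same error.** Protocol 8.1 lets the SAP list the violations that exclude someone from the immunogenicity analysis, and SAP Appendix 1 lists a missed vaccine administration. Whether those sets should instead be visit-specific is a matter of preference.

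**Conclusion.** The contradiction is certain: one population name, two definitions, and safety assigned to it in both documents. Following the SAP would leave out sequential participants who received only the first vaccine, with whatever they reported after it, at about 4 per 1% missing the second out of 400 planned. That the loss falls mainly on the sequential arms is likely from the design, provided missing a separate visit weeks later is more common than missing one of two same-visit injections.

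The effect on the between-group differences cannot be derived from the documents. Over 2 to 10% missing the second vaccine, first-dose reaction rates of 10 to 30% and relative risks of 1 to 3, it runs from 0 to −2.9 points and never reaches the confidence interval half-width. The primary HAI comparison is not affected. This should be corrected before analysis because people who were vaccinated belong in the safety tables, not because a material bias has been shown.

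**What to change.** Change SAP 6.2 so that mITT comprises every randomized participant given at least one study vaccine, matching protocol 8.1, and use that set for all safety analyses. SAP 6.3 and 6.4 state their own both-vaccines requirement, so the immunogenicity sets do not change.

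In each reaction table, show both the number vaccinated at that visit and the number who returned the survey. Reactions come from a self-completed online survey. Using everyone vaccinated as the only denominator would count non-responders as people without reactions.

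If the both-vaccines set is intended, amend protocol 8.1, give the reason, and still report safety in the at-least-one-vaccine set.

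The cost is a one-line SAP change plus a table footnote or column, or a short protocol amendment under the alternative. No new data, visits or assays are needed.

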## 6.3 Influenza Immunogenicity Population

The Influenza Immunogenicity Population is a subset of the mITT Population that includes only subjects who received both vaccines, provide visit 1 and visit 2 blood draws available with HAI titer results for analysis within the protocol-defined time frame, did not have an influenza or SARS-CoV-2 infection between visits 1 and 2, and had no protocol violations affecting immunogenicity. Protocol violations affecting the immunogenicity analyses are defined in the Statistical Analysis Plan (SAP) Appendix 1. The acceptable visit window for sample analysis will be +14 days from the target date. Should 10% or more of the total study population be excluded from the Influenza Immunogenicity Population due to missing the visit window, then an additional analysis will be performed including these subjects with the missing visit window exclusion.

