## 6.4 SARS-CoV-2 Immunogenicity Population

The SARS-CoV-2 Immunogenicity Population is a subset of the mITT Population that includes only subjects who received both vaccines, provide visit 1 and visit 2 blood draws available with MSD results for analysis within the protocol-defined time frame, did not have an influenza or SARS-CoV-2 infection between visits 1 and 2, and had no protocol violations affecting immunogenicity. Protocol violations affecting the immunogenicity analyses are defined in the Statistical Analysis Plan (SAP) Appendix 1. The acceptable visit window for sample analysis will be +14 days from the target date. Should 10% or more of the total study population be excluded from the SARS-CoV-2 Immunogenicity Population due to missing the visit window, then an additional analysis will be performed including these subjects with the missing visit window exclusion.

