## **APPENDIX 1**

### **Protocol Violations for Exclusions from Immunogenicity Analysis**

1. Missed visit/visit not conducted
2. Visit occurred outside of acceptable window
3. No pre- and/or post-vaccination blood draw or insufficient volume for assay analysis for respective vaccine
4. Did not meet inclusion
5. Met exclusion criteria
6. Delayed vaccine administration
7. Missed vaccine administration
8. Study product temperature excursion

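### SAP 6.2 narrows the safety set from at least one vaccine to both, so a missed second dose removes first-dose safety data from the sequential groups only

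*SAP*

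**What the plan says.** **Safety set.** Protocol 8.1: "The mITT population will include any participant who was enrolled, randomized, and received at least one vaccine". The same section assigns safety outcomes to that set. SAP 6.2: "The mITT population will include any participant who was enrolled, randomized, and received both vaccines". SAP 9.2: "Safety endpoints will be assessed using the mITT population". The SAP neither flags nor explains the change.

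**Immunogenicity sets.** Protocol 8.1 again needs one vaccine, plus Visit 1 and Visit 2 blood, and leaves the list of disqualifying violations to the SAP. SAP 6.3 "includes only subjects who received both vaccines, provide visit 1 and visit 2 blood draws available with HAI titer results", and SAP 6.4 "includes only subjects who received both vaccines, provide visit 1 and visit 2 blood draws available with MSD results". Appendix 1 adds "Delayed vaccine administration" (item 6, no length of delay given) and "Missed vaccine administration" (item 7).

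**Schedule.** Group i receives both vaccines on day 0; groups ii and iii receive their second at Visit 2. Under Protocol 5.1, Visit 2 blood is drawn before any Visit 2 dose. All groups get a reaction survey 3 days after Visit 1 (Protocol 5.5.2.1) and weekly questions on hospital admission from day 7 (5.5.2.2). Withdrawals are replaced only before the first dose (5.3.6).

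**The concern.** Membership of the SAP's safety set depends on something that happens after randomization, and for a later dose it can happen only in groups ii and iii. By the time a second dose is missed, the participant's first-dose reaction survey and several weekly admission reports may already be in hand. The rule removes them, and nobody replaces that participant.

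SAP 9.2 reports between-group differences, with 95% confidence intervals, for moderate/severe reactions and for admissions. Protocol 3.2 names increased reactogenicity with concomitant vaccination as something providers should watch for, so this comparison will be read closely. If a bad reaction or an admission after dose 1 makes dose 2 less likely, the rule selectively removes such people from the sequential groups and overstates any excess with concomitant vaccination.

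The same wording touches the primary HAI comparison of group i with group ii (SAP 9.1). A group ii participant who gave Visit 2 blood but then missed the COVID-19 dose has a complete before/after ccIIV4 pair that the missed dose cannot have altered, yet is dropped. Group iii is the mirror case for SARS-CoV-2 titres under SAP 6.4.

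**Working it through.** The plan states no missed-dose rate, reaction rate or power figure, so there is nothing of its own to reproduce. Every rate below is an assumption, shown as a range.

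**Group sizes** (Protocol Summary, adults + children): group i 300 + 100 = 400; groups ii and iii 150 + 50 = 200 each.

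**1. Safety set under each definition.** With p the share of a sequential group missing dose 2, each loses 200p. If everyone receives all day-0 doses, the protocol definition keeps 400/200/200 whatever p is.

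| p | lost per sequential group | SAP safety set (i/ii/iii) |
|---|---|---|
| 2% | 4 | 400/196/196 |
| 5% | 10 | 400/190/190 |
| 10% | 20 | 400/180/180 |

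**2. Effect on the day-0 reaction rate.** Let r be the true moderate/severe rate after the day-0 dose, and k the ratio of the rate in people who miss dose 2 to r. Then observed rate = (r - p·k·r)/(1 - p). With r = 20%:

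| p | k = 2 | k = 3 |
|---|---|---|
| 2% | (0.20 - 0.008)/0.98 = 19.6% | (0.20 - 0.012)/0.98 = 19.2% |
| 5% | (0.20 - 0.020)/0.95 = 18.9% | (0.20 - 0.030)/0.95 = 17.9% |
| 10% | (0.20 - 0.040)/0.90 = 17.8% | (0.20 - 0.060)/0.90 = 15.6% |

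The fall is 0.4 to 4.4 points. With k = 1 it is zero. It scales with r: 0.2-2.2 points at r = 10%, 0.6-6.7 at r = 30%. For comparison, the 95% half-width for i vs ii at r = 20% is 1.96 × sqrt(0.2 × 0.8 × (1/400 + 1/200)) = 6.8 points.

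**3. Any-dose regimen endpoint.** SAP 9.2 does not say whether groups are compared per visit or over the whole regimen. Take 20% per dose, independent, p = 5%, k = 2. Among those with both doses: 1 - (1 - 0.1895) × 0.80 = 35.2%. With everyone retained: 0.95 × 35.2% + 0.05 × 40% = 35.4%. The difference is about 0.2 points.

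**4. A single admission.** One admission after dose 1 followed by no dose 2 turns 1/200 (0.5%) into 0/199 in a sequential group. The same event in group i stays 1/400.

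**5. HAI, group i vs group ii.** The rule itself removes only people bled at Visit 2 and then not dosed; those with no Visit 2 blood leave under either document. If 25-50% of those who miss dose 2 still gave blood, the share lost is q = 2% × 25% = 0.5% up to 10% × 50% = 5%, or 1-10 of 200.

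- Standard error ratio = sqrt(1/400 + 1/(200(1 - q))) / sqrt(1/400 + 1/200) = 1.002 to 1.017.
- If those removed differ f-fold in titre from those kept, the group ii GMT shifts by f^q: 1.5^0.005 = 1.002 up to 2^0.05 = 1.035, in either direction. If they do not differ, it does not shift.

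**The case against.** **Safety is an exploratory, descriptive objective, and the size of the bias is entirely assumed.** This stands. The 4.4-point figure needs 10% missed doses and a 60% moderate/severe rate in those people, and it still lies inside the 6.8-point half-width. A reader might infer that the rule will make sequential vaccination look safer. The documents do not support that as a fact, because the direction requires missing to be related to first-dose harm.

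**Keeping one-dose participants creates its own distortion.** On a whole-regimen endpoint they had one exposure, so they lower the apparent sequential burden. This is fair. It argues for per-visit denominators, not for deleting first-dose data.

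**The loss counts are upper figures, and group i is not immune.** Some surveys go unanswered, and participants who withdraw may have their data removed (Protocol 5.3.6); both happen under either definition. A group i participant given one injection would also fail the SAP rule. These points stand, but such a person missed a co-administered dose; a missed later dose is possible only in groups ii and iii.

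**The SAP was entitled to narrow the immunogenicity sets.** This is largely right. Protocol 8.1 delegates the violation list, item 7 is on it, and the same population serves the Visit 3-4 waning analyses, where both doses can matter. The unannounced departure is therefore much clearer in 6.2 than in 6.3 and 6.4. A reader might also infer that the primary HAI result is materially biased. Step 5 does not support that, and group iii is not in that comparison.

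**The exclusions will be visible.** SAP 8.1 reports a breakdown of the analysis populations. That shows the counts but does not restore the outcomes. The ITT set is assigned demographics only, and the 10% trigger in 6.3 and 6.4 covers missed visit windows, not missed doses.

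**Conclusion.** The point holds as a conflict in current text with an arm-dependent consequence. SAP 6.2 contradicts Protocol 8.1 on the set used for safety, and a missed Visit 2 dose then removes first-dose reaction and admission data from groups ii and iii only. That much follows from the documents without any assumed rate.

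The size does not. Under the stated assumptions the day-0 moderate/severe rate is understated by 0.4-4.4 points, by about 0.2 points on an any-dose endpoint at 5% missed and a 2-fold rate, and by nothing if missing is unrelated to reactions. Admissions are likely to be few, so one removed event can change what is reported.

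The titre effect is confined to group ii for HAI (group iii for SARS-CoV-2) among people bled but not dosed at Visit 2, and is probably very small. It is worth correcting because the exclusion has no bearing on the sample analysed, not because it threatens the primary result.

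**What to change.** 1. **SAP 6.2.** Restore the protocol's requirement of at least one vaccine for the safety set. In SAP 9.2, report reactions per vaccination visit, with those dosed at that visit as the denominator.
2. **SAP 6.3 and 6.4.** Require the vaccine under analysis and its pre- and post-dose samples. For HAI in group i vs group ii, that is ccIIV4 on day 0 with Visit 1 and Visit 2 blood. Keep the both-vaccines set as a labelled sensitivity analysis, and for Visit 3-4 analyses where both doses matter.
3. **Appendix 1, items 6 and 7.** Apply them only to doses that can affect the sample analysed. A missed or delayed Visit 2 dose can affect later titres, not blood drawn before it. Without this step, item 7 would still exclude these participants even if 6.3 and 6.4 were corrected.

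All three are SAP text edits. They need no new data and no change to study procedures, and step 1 returns to what the protocol already says. If the sponsor prefers both vaccines for safety, the SAP should declare and justify the departure.
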